## 5. AMENDMENTS AND UPDATES

A pilot e-CRF study may be conducted before the main study to evaluate the feasibility of the methods to establish a Zimino® registry. A protocol amendment may be prepared accordingly.

## 6. MILESTONES

Milestone	Planned date
First Patient In	January, 2020
Last Patient In	January, 2021
Last Patient Out	April, 2021
Interim report	NA
Final Data base lock	July, 2021
Final report of study results	October, 2021

## 7. RATIONALE AND BACKGROUND

### 7.1 Background

The French National Authority for Health (Haute Autorité de Santé) requested a registry study to obtain post-market surveillance data to describe baseline clinical profiles, management and hospital outcome of patients treated with Zimino®.

### 7.2 Rationale

There is an increased interest in the use of real-life data to observe how new medicines are used in clinical practice. A properly designed registry can provide real-life view of clinical practice, patient outcomes, safety and effectiveness.

This study is designed to provide real-life data on the use, safety and clinical outcomes of Zimino® in clinical practice in France.

## 8. RESEARCH QUESTION AND OBJECTIVES

In this real-life, multicentre study, patients treated with Zimino® will be followed for 90 days after discharge from the hospital

The primary objective is to provide real-life follow-up data on patients who have been treated with Zimino® in France.

The secondary objectives are:

- To describe the use of concomitant inotropes during hospitalisation.
- To assess re-hospitalisations at 90 days after discharge.
- To evaluate tolerance and serious adverse events (SAEs) during hospitalisation
- To assess mortality during hospitalisation and at 30 and 90 days after discharge.

## 9. RESEARCH METHODS

### 9.1 Study design

This is a real-life, multicentre study in patients treated with Zimino® in a real-life setting.

[figure not shown]
Each patient will be treated as decided by the physician according to current local clinical practice. The decision to prescribe Zimino® to the patient is made by the physician in charge, regardless of the possibility to include the patient in the study. The informed consent may be obtained at any time during hospital stay, before or after the start of Zimino® .

The patients will be evaluated during the index hospitalisation and at day-30 and day-90 after discharge. The follow-up can be done via a phone call, or a visit to the hospital. The study design is presented in .

Figure 1.

The estimated enrollment period is 12 months (enrollment of the first patient – enrollment of the last patient), or less if the cohort (n=600) is completed earlier, and the maximum total data collection period is 15 months.

Figure 1. Study design

## **9.2 Setting**

### **9.2.1 Hospitals**

France-Levo will enroll 600 consecutive patients receiving levosimendan at all French sites where Zimino® is prescribed.

### **9.2.2 Study population**

The study will enrol 600 patients in France.

To ensure that patients are captured in a representative way and to avoid selection bias issues, study participation will be proposed to all consecutive patients who have received Zimino® during the recruitment period. The hospitals will stop recruitment once data from 600 patients have been collected.

All available information regarding patients receiving Zimino® but not entered into the registry will be collected.

#### **9.2.2.1 Inclusion criteria**

Patients are eligible to be included in the study if all of the following criteria apply:

1. Patients receiving Zimino®.
2. Patients or patient's families not objecting to the patient's participation in the study.

#### **9.2.2.2 Exclusion criteria**

None.

#### **9.2.2.3 Removal of patients from assessments**

Patients are free to discontinue the study at any time without providing a reason. However, the investigator should try to identify the reason and document it in the case report form (CRF).

The study monitor should be notified about premature discontinuations. If the discontinuation is due to an SAE, the study monitor should be notified by investigator within 24 hours.

### **9.2.3 Medicinal product**

Current clinical practice use.

### **9.2.4 Study procedures**

The prospective follow-up data will be obtained on days 30 and 90 after discharge by calling the patient or a patient's family member, or during a visit to the hospital if the patient is hospitalized or comes for a scheduled consultation. Follow-up data may also be obtained by review of medical records.

For patients who have been transferred to another hospital, follow-up data will be collected by contacting the respective hospital according to local practice. For patients who have been discharged home or to another care facility, follow-up data will be collected by contacting the patient or the patient's family. Every effort will be made according to local practice to ensure that the patient is alive before contacting the patient's family.

Table 1 lists study procedures and indicates with an 'x' during which visit a particular procedure is performed.

Table 1. Schedule of study procedures

	During index hospitalisation	During follow-up	
		30 ( $\pm$ 15) days after discharge	90 ( $\pm$ 15) days after discharge
Patient identification	x		
Informed consent	x		
Inclusion criteria	x		
Demographic characteristics	x		
Hospital and ICU/CCU admission dates	x		
Reason for hospitalisation	x		
Cardiogenic shock	x		
Zimino® treatment	x		
Concomitant inotropes	x		
Chronic atrial fibrillation	x		
Pre-existing amiodarone	x		
Pre-existing dialysis	x		
Pre-existing mechanical assistance	x		
Tolerance	x		
SAEs	x	x	x
Mortality	x	x	x
ICU/CCU and hospital discharge dates	x		
Re-hospitalisations		x	x

ICU = Intensive care unit; CCU = Coronary care unit; SAE = Serious adverse event

### 9.3 Variables to be collected

Data will be collected for all patients and recorded on the CRFs as follows:

#### 9.3.1 Demographic and baseline characteristics

- Age,
- Sex
- Date of admission to the hospital

- Date of ICU/CCU admission
- SAPS II score (= IGS2)
- SOFA score on ICU admission
- Reason for hospital admission (pop-up menu) [1) medical HF decompensation, 2)surgical cardiac procedure, 3)other ICU admission (text)]
- Did the patient have cardiogenic shock (yes/no)?
  - If yes, date of the first symptoms of the cardiogenic shock

### **9.3.2 Zimino® treatment**

- Indication for the use of Zimino® pop-up menu: 1) cardiogenic shock (medical setting or post cardiac surgery), 2) Heart failure decompensation (medical, setting), 3) Low cardiac output syndrome (post cardiac surgery), 4) heart failure decompensation in a patient receiving beta-blockers, 5) ECMO weaning, 6) repetitive use in a patient with end-stage heart failure, 7) other (text)
- SOFA score on the day of ZIMINO® initiation
- Start of Zimino® treatment (start date and hour)
- Dose ( $\mu\text{g}/\text{kg}/\text{min}$ ) and total dose (mg) of Zimino®
- Was bolus injection of Zimino® administered (yes/no)?
- End of Zimino® treatment (stop date and hour)

### **9.3.3 Concomitant inotropes**

- Use of other inotropes (yes/no)
  - Dobutamine,
    - Start of dobutamine (date and hour)
    - Maximal dose of dobutamine
    - End of dobutamine (stop date and hour)
  - Noradrenaline
    - Start of noradrenaline (date and hour)
    - Maximal dose of noradrenaline
    - End of noradrenaline (stop date and hour)
  - Adrenaline
    - Start of adrenaline (date and hour)

- Maximal dose of adrenaline
- End of adrenaline (stop date and hour)
- Milrinone
- Start of milrinone (date and hour)
- Maximal dose of milrinone
- End of milrinone (stop date and hour)

#### **9.3.4 Chronic atrial fibrillation**

- Chronic atrial fibrillation (yes/no)
- Pre-existing treatment with amiodarone before the start of Zimino® (yes/no)

#### **9.3.5 Pre-existing dialysis**

- Pre-existing dialysis before the start of Zimino® (yes/no). If yes,
  - Date of weaning (or death)

#### **9.3.6 Pre-existing mechanical assistance**

- Pre-existing mechanical assistance before the start of Zimino® (yes/no). If yes,
  - Date of insertion
  - Type of mechanical assistance
    - Venoarterial extracorporeal membrane oxygenation (VA ECMO) (central or peripheral)
    - Veno-venous ECMO (VV ECMO)
    - Impella® 5.0, Impella® 2.5) or Impella CP
    - Intra-aortic balloon pump (IABP)
    - Berlin Heart EXCOR
  - Date of weaning (or death)

#### **9.3.7 Tolerance**

- Hypotension during and after the start of Zimino® (yes/no).
  - If yes, was noradrenaline started or its dose increased? (yes/no).
  - Duration of hypotension (minutes, hours)

- New atrial fibrillation after the start of Zimino® (yes/no)? If yes,
  - Was amiodarone given? (yes/no).
  - Was beta-blocker given ? (yes/no)
  - Was cardioversion performed?
  - Persistent AF? (yes or no)
  - If transient, duration of AF (min, hours, days)

### **9.3.8 Serious adverse events during and after the start of Zimino® (regardless of causal relationship to Zimino)**

SAEs will be collected regardless of causal relationship of the event to Zimino® treatment:

- MACE defined as death of cardiac origin, stroke, myocardial infarction, heart rhythm disorder requiring external electrical cardioversion (EEC) or cardiogenic pulmonary oedema
- Death of non cardiac origin
- Mechanical assistance : Start date and date of weaning
- Dialysis : Start date and date of weaning
- Any other event engaging the vital prognosis, including septic shock and digestive haemorrhage
- Date of start event, end of event or ongoing

For all the variables above, duration of the event will also be recorded.

### **9.3.9 Mortality**

Time of death and cause of death will be recorded up to follow-up day 90.

### **9.3.10 Length of ICU/CCU and hospital stay**

- Date of ICU/CCU discharge.
- Hospital-free days at day-30 and day-90
- Date of hospital discharge

The length and clinical aspects of the hospital and CCU/ICU stay before starting Zimino® are expected to vary widely among patients. Therefore, all length of stay endpoints are primarily measured from the time of starting Zimino® treatment.

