## 4. ABSTRACT

Title France Zimino® registry: A French registry evaluating the use of levosimendan (Zimino®)

Protocol version and date V1, 08 November 2019

Rationale and background The French National Authority for Health (Haute Autorité de santé) requested a registry study to obtain post-market surveillance data to describe baseline clinical profiles, management and outcome of patients treated with Zimino®. This study is designed to provide real-life data on the use, safety and clinical outcomes of Zimino® in routine clinical practice in France.

Research question and objectives Primary objective:
 
 
• To provide real-life follow-up data on patients who have been treated with Zimino® according to local routine clinical practice in France.
 
 
Secondary objectives:
 
 
• To describe the use of concomitant inotropes during hospitalisation.
 
• To assess re-hospitalisations 30 and 90 days after hospital discharge.
 
• To evaluate tolerance and serious adverse events (SAEs) during hospitalisation.
 
• To assess mortality 30 and 90 days after hospital discharge.
 

Primary endpoints
 
 
• Indication for Zimino®.
 
• Dose and duration of treatment with Zimino®.
 
• Length of intensive care unit / coronary care unit (ICU/CCU) stay from the start of Zimino®.
 
• Length of hospital stay from the start of Zimino®.
 

Secondary endpoints
 
 
• Concomitant inotropes during hospitalisation.
 
• Re-hospitalisations 30 and 90 days after hospital discharge.
 
• Tolerance, as assessed by hypotension and atrial fibrillation during hospitalisation.
 
• SAEs, including major cardiovascular events (MACEs), mechanical assistance, dialysis or any other event engaging the vital prognosis during hospitalisation.
 
• Mortality during hospitalisation 30 and 90 days after hospital discharge.
 

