
Study design This is a real-life, non-interventional, observational, multicentre study in all patients (including children) receiving Zimino® in France. The patients will be evaluated during the index hospitalisation and on follow-up days 30 (±15) and 90 (±15) after hospital discharge. The follow-up can be a phone call or a visit to the hospital. Patients who meet the eligibility criteria will be identified consecutively at each hospital. The participating hospitals will vary in size and medical activities, depending on their location and the population size they serve. The physician will determine the patient's treatment strategy. Drug prescriptions and the indications to perform diagnostic or therapeutic procedures will be left completely to the discretion of the physicians. The estimated enrollment period is 12 months (enrollment of the first patient – enrollment of the last patient), or less if the cohort (n=600) is completed earlier, and the maximum total data collection period is 15 months.

Population
 
Inclusion criteria:
 
 
• Patients receiving Zimino® treatment.
 
• Patients or patient's families not objecting to the patient's participation in the study.
 
 
Exclusion criteria: None

Medicinal product, dose and mode of administration
 
Zimino® 2.5 mg/ml concentrate for solution for infusion. Dose and duration of treatment will be at the discretion of the physicians.

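### The primary ICU/CCU-stay endpoint is clocked from Zimino start with one listed admission and one discharge date, so ward days can count as ICU/CCU days and returns to the unit cannot be measured

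*Protocol*

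**What the plan says.** The Abstract lists four primary endpoints. One is "Length of intensive care unit / coronary care unit (ICU/CCU) stay from the start of Zimino"; another is length of hospital stay from the same origin. Section 9.3.10 explains that the stay before treatment is expected to vary widely between patients and concludes: "Therefore, all length of stay endpoints are primarily measured from the time of starting Zimino® treatment".

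The listed variables that bear on this endpoint are:

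- section 9.3.1: "Date of ICU/CCU admission";
- section 9.3.2: start and stop of Zimino, each with date and hour;
- section 9.3.10: "Date of ICU/CCU discharge".

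The Abstract describes a "multicentre study in all patients (including children) receiving Zimino® in France". The only treatment-related inclusion criterion in section 9.2.2.1 is "Patients receiving Zimino", and section 9.2.2.2 has no exclusions. Section 9.2.1 takes in every French site that prescribes the drug. The indications in section 9.3.2 run from cardiogenic shock and ECMO weaning to medical heart failure decompensation and "6) repetitive use in a patient with end-stage heart failure". No section requires an ICU/CCU stay, or that the infusion be started there.

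**The concern.** Starting the clock at treatment works for hospital stay, because these patients are in hospital when Zimino starts. ICU/CCU stay is different. The interval from Zimino start to ICU/CCU discharge equals ICU/CCU time only if the patient is in the unit when the infusion starts and leaves it once. The protocol does not guarantee either condition.

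Two problems follow. If Zimino starts before ICU/CCU entry, the ward days in between fall inside the interval. If the patient returns to the unit during the index stay, one admission date and one discharge date cannot describe two periods.

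At stake is the accuracy of a primary endpoint in a study whose whole purpose is description. The endpoint is also to be summarised by indication. If starts outside the unit or returns to it are more frequent in some indications than in others, the errors would not cancel in that comparison. The documents do not show whether they are.

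**Working it through.** The protocol gives no expected value, variance or worked example for ICU/CCU stay, so there is no figure of its own to reproduce. The precision calculation in section 9.5 concerns a proportion of 50% and does not bear on this point.

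**Inputs.** From the protocol: the origin (Zimino start), the single listed ICU/CCU admission date and the single listed discharge date. The patient courses below are assumed illustrations.

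**Two measures compared.**

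- Literal reading: ICU/CCU discharge date minus Zimino start date.
- ICU/CCU time after start: for each ICU/CCU period, discharge minus the later of admission and Zimino start (zero if that is negative), summed over periods.

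| Assumed course (days) | Literal reading | ICU/CCU days after start |
|---|---|---|
| ICU 0-8, Zimino day 2 | 8 - 2 = 6 | 8 - 2 = 6 |
| ICU 3-8, Zimino on ward day 0 | 8 - 0 = 8 | 8 - 3 = 5 |
| ICU 0-3 and 8-12, Zimino day 0 | 3 (first discharge) or 12 (last) | 3 + 4 = 7 |
| ICU 0-5 and 9-14, Zimino day 1 | 5 - 1 = 4 or 14 - 1 = 13 | 4 + 5 = 9 |
| ICU 0-4, Zimino on ward day 6 | 4 - 6 = -2 | 0 |
| Never in ICU/CCU | no value | 0 |

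The two measures agree in the first row only.

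**Which errors can be repaired from the listed dates?**

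- Start before entry (row 2): yes, by counting from the recorded admission date. The stated origin would have to be overridden.
- Return to the unit (rows 3 and 4): no. In row 3, using the last discharge counts 8 - 3 = 5 ward days as ICU/CCU days, since 12 - 7 = 5. Using the first discharge loses the 4 days of the second period. Neither 8 (second admission) nor whichever discharge date was not kept is a listed variable.
- Start after discharge, or never in the unit (rows 5 and 6): yes. The existing dates identify both groups, and the value can be set to 0 or not applicable.

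**Do other sections capture a return?** Section 9.3.11 covers readmission to hospital after discharge, not a return to the unit during the index stay. The plural dates in the Abstract and in Table 1 cover hospital and ICU/CCU together, so they do not establish repeated ICU/CCU periods. Section 9.7.3 does not define the endpoint further.

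**The case against.** The strongest reply is that this is endpoint derivation, which belongs in an analysis plan. The ordinary meaning of ICU/CCU stay from a given origin is time in the unit after that origin. On that meaning ward days never count and a length cannot be negative. The protocol nowhere writes the subtraction used above. This largely disposes of starts after ICU/CCU discharge and of patients never admitted there. A reader might infer that the endpoint yields negative or undefined values, or that less ill patients vanish from a primary endpoint. The documents do not support that: the listed dates are enough to set these patients to 0 or not applicable, and length of hospital stay still covers them.

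It can also be said that the eCRF is not shown. Section 9.3.11 lists the rehospitalisation dates in the singular, although the Abstract asks for the number of rehospitalisations, so singular wording need not mean a single entry. That is fair: a single date pair is an inference from the variable list. Still, the Abstract's request makes repetition explicit for rehospitalisations, and nothing does the same for ICU/CCU periods.

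Finally, the variables lean towards an ICU population (SAPS II, SOFA at ICU admission, a category for other ICU admissions). That suggests few starts outside the unit, but it does not touch returns to it, and eligibility does not impose it.

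**Conclusion.** The point holds for two situations. When Zimino starts before ICU/CCU entry, the stated origin read literally adds the ward days (8 against 5 in the example). When a patient returns to the unit during the index stay, the listed dates cannot give the right value (3 or 12 against 7). The second matters more, because it is a limit of data capture that a later analysis plan cannot undo.

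The day counts are illustrations. The conclusion rests on reading the variable list as one date pair per patient and the origin as applying to everyone. A reader might go further and estimate what share of the 600 patients has a wrong value, or conclude that comparisons between indications are biased. The documents give no frequency of starts outside the unit or of returns to it, overall or by indication, so neither step is supported. The study is descriptive with no confirmatory hypothesis, so no test result is at risk. This is a correction worth making to a primary endpoint, not a flaw that undermines the registry.

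**What to change.** - In the Abstract and section 9.3.10, define the endpoint as ICU/CCU days on or after the start of Zimino. For each ICU/CCU period in the index stay, count from the later of ICU/CCU admission and Zimino start to ICU/CCU discharge, and sum the periods.
- Report patients with no ICU/CCU time after the start as a separate proportion.
- State in sections 9.3.1 and 9.3.10 that the ICU/CCU admission/discharge date pair is repeatable within the index stay, and build the eCRF accordingly.

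A separate item for where Zimino was started is not needed, because the Zimino start and the ICU/CCU dates largely show it.

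The cost is one reworded definition, one repeatable date pair and slightly more data entry for patients with more than one ICU/CCU period. The change should be in place before data collection. Afterwards, the missing periods could be obtained only by going back to the medical records.

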### 9.3.11 Re-hospitalisations up to 30 ( $\pm 15$ ) and 90 ( $\pm 15$ ) days after hospital discharge

- Was the patient re-admitted to the hospital (yes or no)
- If yes: date of admission
- If yes: date of discharge
- Main reason for re-hospitalisation
- Re-administration of Zimino® (yes/no)

## 9.4 Data sources

Data will be collected from medical records and follow-up interviews and entered into the eCRFs.

## 9.5 Study size

The study will enrol 600 patients in France.

This sample size will allow to describe a proportion of 50% (most conservative hypothesis) with a precision to at least 4.5% with an estimation of non available data fom 10 to 20%.

Hypothesis	Proportion	$\alpha$	accuracy	N	% Non available data	N total
Scenario 1	50,00%	5%	4,5%	475	10%	523
Scenario 2	50,00%	5%	4,5%	475	15%	547
Scenario 3	50,00%	5%	4,5%	475	20%	570

## 9.6 Data management

Data to be collected according to the study protocol (and amendments, if any) will be recorded into an electronic data capture (EDC) system using eCRFs at the site.

Investigators and other relevant site personnel will be trained to use the EDC system. After completion of training, they are provided with user names and authorised access to enter and correct data on the eCRFs.

Individual data fields in the EDC system may be locked on an ongoing basis during the study. The fields may be unlocked if further updates are needed. When all data have been entered and all queries resolved, the whole database will be locked.

## 9.7 Data analysis

Statistical analyses, tables and patient data listings will be performed with SAS® for Windows 9.4 or later (SAS Institute Inc., Cary, NC, USA). Statistical analysis will be performed by or under the supervision of the sponsor.

### **9.7.1 Statistical hypotheses**

No specific statistical hypothesis that would be evaluated in a confirmatory manner is specified in this study or against any historical control. Instead, the emphasis is on estimation and exploratory analyses.

No inferential statistics will be performed.

### **9.7.2 Analysis populations**

All enrolled patients who have received Zimino® will be included in the analysis. All available data will be analysed.

### **9.7.3 Statistical analyses**

The variables will be evaluated by frequency tables and summary statistics, as applicable. Variables will be summarised also by indication for the use, if feasible. For categorical variables, proportions and 2-sided 95% confidence intervals will be presented.

For the primary objective, all clinical and sociodemographic characteristics (age, sex, clinical scores) use of Zimino treatment (indication, dose, duration, routes) will be described at each available time point.

For secondary objectives, use of concomitant inotropes during the hospitalisation (percentage of patient, duration etc...) will be described, as well as rate of patient rehospitalised at 90 days after discharge.

For safety and tolerance analysis, description of hypotension, new atrial fibrillation will be done as well as all SAEs occurred during and after Zimino® treatment.

Rate of mortality will be calculated and described.

If applicable, the potential differences between indications of Zimino® will be tested in an exploratory way, as no statistical hypothesis have been done. Additional subgroup analyses may be performed based on the observed data.

